## First Follow Up Survey

1. Today's date:    /    / 20
2. How tall are you? \_\_\_\_\_ (feet, inches)
3. What is your weight? \_\_\_\_\_ (pounds)
4. Do you have any history of any of the following (check box if Yes):

Heart attack

Liver disease:

Congestive heart failure

.. Mild liver disease

.. Moderate or severe liver disease

Peripheral vascular disease

Diabetes:

Cerebrovascular disease

.. Diabetes without chronic complications

Hypertension

.. Diabetes with chronic complications

Chronic pulmonary disease

Hemiplegia or paraplegia

Rheumatologic disease

Renal disease

Peptic ulcer disease

Any other malignancy besides prostate cancer, including leukemia and lymphoma

Metastatic (non-prostate) solid tumor

5. What was your last PSA value? (approximate value): \_\_\_\_\_ ng/ml

Don't know

6. When was the date of your last PSA? (approximate date): \_\_\_\_\_ / \_\_\_\_\_

Month Year

Don't know

7. **PSA:** How true has each of the following statements been for you during the past 4 weeks?

*Choose one response on each line*

	Not at all	A little bit	Somewhat	Quite a bit	Very much
a. I keep close track of my PSA					
b. Knowing my PSA level is comforting to me					
c. I live in fear that my PSA will rise					

8. Since your initial treatment for prostate cancer, did your doctor ever tell you that your prostate cancer came back (recurred) or progressed (got worse)?

Yes  
 No

9. Since you were diagnosed with prostate cancer, has a doctor ever told you that your prostate cancer had spread to other areas of your body?

Yes  
 No

10. These next questions are about the treatments for prostate cancer **that you have received.**

*For each of the following types of treatment, please check the one(s) you have received and indicate the date you received it (or started it)*

Type of Treatment	I have received this treatment	Date received or started
a. Active Surveillance (My doctor will monitor how I am doing without directly treating the cancer)		____ / ____ / ____ M M   D D   Y Y
b. Prostate surgery (radical prostatectomy) , which would remove the whole prostate.		____ / ____ / ____ M M   D D   Y Y
c. HIFU / High Intensity Focused Ultrasound (ultrasound waves cross tissue to destroy the part of the prostate that had cancer)		____ / ____ / ____ M M   D D   Y Y
d. Cryotherapy (freezing the part of the prostate that had cancer)		____ / ____ / ____ M M   D D   Y Y
e. Laser therapy		____ / ____ / ____ M M   D D   Y Y
f. Radio Frequency Ablation		____ / ____ / ____ M M   D D   Y Y

Type of Treatment	I have received this treatment	Date received or started
g. Photodynamic therapy		____/____/____ MM DD YY
h. External Beam Radiation Therapy or IMRT (radiation treatment requiring more than 2 weeks of treatment)		____/____/____ MM DD YY
i. Stereotactic Body Radiation Therapy (SBRT) (radiation treatment requiring less than 2 weeks of treatment)		____/____/____ MM DD YY
j. Brachytherapy (radioactive seeds) This involves having radioactive seeds placed within the prostate		____/____/____ MM DD YY
k. Proton Beam Therapy		____/____/____ MM DD YY
l. Any other type of radiation therapy? Describe: _____		____/____/____ MM DD YY
m. Hormonal treatments to lower testosterone (e.g. Lupron, Zoladex, Firmagon, Eligard, Vantas, etc)		____/____/____ MM DD YY
n. Surgical removal of testicles (Orchiectomy)		____/____/____ MM DD YY
o. Chemotherapy (docetaxel, cabazitaxel, other)		____/____/____ MM DD YY

**If you have only received active surveillance or have not had any treatment yet for your prostate cancer, please skip to Question 16.**

11. As individuals go through treatment for cancer, they sometimes experience different symptoms and side effects. For each symptom below, please select the one response that best describes your experiences in the 7 days after your initial treatment choice (surgery, radiation, partial gland ablation).

1) Symptom: Abdominal pain				
a. In the 7 days after your initial treatment, how often did you have pain in the abdomen (belly area) ?				
 Never	 Rarely	 Occasionally	 Frequently	 Almost constantly
b. In the 7 days after your initial treatment, what was the severity of your pain in the abdomen (belly area) at its worst ?				
 None	 Mild	 Moderate	 Severe	 Very severe

c. In the 7 days after your initial treatment, how much did **pain in the abdomen (belly area) interfere** with your usual or daily activities?

Not at all       A little bit       Somewhat       Quite a bit       Very much

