	Change from Baseline in Ejaculatory Function as Measured on MSHQ-EjD at 8 Months & 12 Months following Treatment
	Change from Baseline in Patient-Reported Anxiety as Measured on MAX-PC at 8 Months & 12 Months following Treatment
	Assessment of Treatment Regret as Measured on Clark's Prostate Cancer Health Worry at 8 Months & 12 Months following Treatment
	Assessment of Adverse Events at 8 Months & 12 Months following Treatment by CTCAE v5.0
	Assessment of Cancer Recurrence at 8 Months & 12 Months following Treatment by Patient Medical Records

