### 1.1. Objectives

To measure the self-reported, overall and disease specific health related quality of life (HRQOL) prior to treatment, at 8 months, and 12 months following active surveillance (AS), SBRT, IMRT, PGA, and RP.

To define and compare the rate of adverse events following stereotactic body radiation therapy (SBRT), partial gland ablation (PGA), intensity modulated radiation therapy (IMRT) and radical prostatectomy (RP) among men recently diagnosed with low and intermediate risk prostate cancer.

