## 6. Study Procedures

### 6.1 Schedule of Trial Events

Data elements	Baseline	8 months	12 months
Patient reported			
Income	X		
Education	X		
Family history of prostate cancer	X		
Employment status	X	X	X
Charlson co-morbidity	X	X	X
Height	X	X	X
Weight	X	X	X
Medications	X	X	X
Treatment (confirm PGA and SBRT)			
Cancer recurrence		X	X
Secondary treatment(s)		X	X
Adverse events		X	X
Patient reported outcomes	X	X	X
Registry reported			
Age	X		
Race	X		
Marital status	X		
Insurance type	X		
Poverty level based on census tract	X		
PSA	X		
Biopsy pathology	X		
Clinical stage	X		
Treatment	X		

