**46. Are there any other issues or concerns about your prostate cancer or your treatment that you would like to mention?**

---

---

**Thank you very much for completing this survey. Please return in one of the enclosed postage paid envelopes or mail to address on front of survey.**

**Please also review and complete the HIPAA form if you agree to provide authorization for us to review your medical records regarding your prostate cancer and treatment.**

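### The primary cancer recurrence endpoint has two conflicting sources, and the survey items that could supply it merge recurrence with progression in one undated Yes/No also put to active surveillance and untreated men

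*Combined protocol and SAP*

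**What the plan says.** The last primary endpoint in the Protocol Summary reads "Assessment of Cancer Recurrence at 8 Months & 12 Months following Treatment by Patient Medical Records". It defines no event and names no groups.

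The Schedule of Trial Events (6.1) has a row "Cancer recurrence" under its patient-reported block, marked at 8 and 12 months. The registry-reported block has no such row, and the registry variables to be linked under 3.2 do not include recurrence.

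In Appendix A, Q8 of the First Follow Up Survey begins "Since your initial treatment for prostate cancer, did your doctor ever tell you" and asks in one Yes/No whether the cancer recurred or progressed: "did your doctor ever tell you that your prostate cancer came back (recurred) or progressed (got worse". It asks for no date and offers no not-applicable option. Q5 of the Second Follow Up Survey is worded the same way.

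The treatment grid follows as Q10 at 8 months and Q7 at 12 months. It lists active surveillance (AS) first among the types of treatment, allows several ticks and asks for a date on each row. Only after Q10 comes the instruction "If you have only received active surveillance or have not had any treatment yet for your prostate cancer, please skip to Question 16". The 12-month survey has no such skip before Q5.

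Section 8 describes models for patient-reported outcomes and adverse events, and none for recurrence. Sections 1.1 and 1.2 do not mention recurrence.

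**The concern.** Recurrence after treatment and progression under surveillance are different events. The first needs a treatment after which cancer returns. The second happens while the cancer is still in place. A single tick box records both as the same answer.

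If records are the source, this item matters little. If patient report is the source, as the schedule has it, or fills gaps in the records, the merged item becomes the outcome. The plan does not say which. At stake is a primary endpoint on cancer control in which some counted events may have happened before the treatment they are attributed to.

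**Working it through.** The plan states no rate, count or power for recurrence, so there is no figure to reproduce. The check is mainly of the text, with an illustration of size.

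**1. Source.** The Protocol Summary says medical records and section 6.1 says patient reported. Nothing says which prevails or how disagreements are settled.

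**2. Who answers.** At 8 months the order is Q8 (recurred or progressed), Q10 (treatment grid), then the skip to Q16. The skip removes Q11 to Q15 only, so AS-only and untreated men have already reached Q8. At 12 months Q5 comes before Q7 with no skip. The endpoint's reference to following treatment does not clearly exclude AS, because the quality-of-life objective in 1.1 speaks of outcomes "following active surveillance (AS), SBRT, IMRT, PGA, and RP".

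**3. What a Yes can be resolved to**, using the grid and linked registry treatment dates:

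- *AS only:* identifiable. A Yes can sensibly mean only progression.
- *No treatment yet:* identifiable. A Yes cannot be recurrence after treatment.
- *AS, then active treatment before the survey:* the treatments are dated but the Yes is not. It may be progression that led to treatment, or recurrence after it.
- *Active treatment only:* the Yes may mean recurred or progressed, and one box cannot separate them. Spread has its own item (Q9 at 8 months, Q6 at 12 months), which narrows but does not remove the ambiguity.

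The last two groups cannot be repaired in analysis from self-report.

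**4. Illustration of size.** Group sizes are from section 8: AS 300, PGA 280, SBRT 288, IMRT 316, RP 333. All rates below are assumptions.

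(a) *Switchers counted in a treated group.* Let r be true recurrence and s the share of the group who were told of progression on AS and then switched. If no man falls in both, the recorded rate is r + s. For RP:

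- r = 1%, 3%, 5%: 333 × r = 3.3, 10.0, 16.7 true recurrences.
- s = 1%, 3%, 5%: 333 × s = 3.3, 10.0, 16.7 further Yes answers.
- Recorded rate: from 1% + 1% = 2% (6.7 men) to 5% + 5% = 10% (33.3 men).

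If s = 0 there is no distortion. Between treated groups, direction depends on which one takes in more switchers.

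(b) *Yes answers tabulated as one outcome without using the grid.* The total is 300 + 280 + 288 + 316 + 333 = 1,517, so 1,517 − 300 = 1,217 are treated. Let g be the share of AS men told of progression. The AS share of all Yes answers is 300g / (300g + 1,217r).

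- r = 5%, g = 5%: 15 / (15 + 60.9) = 20%, which equals the AS share of men (300 / 1,517 = 19.8%). The group rates do not differ.
- r = 3%, g = 10%: 30 / (30 + 36.5) = 45%, with rates 7 points apart.
- r = 1%, g = 20%: 60 / (60 + 12.2) = 83%.

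The result runs from no visible difference to a large one, wholly according to rates the documents do not give.

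**The case against.** The strongest reply is that the endpoint's stated source is the medical record, so the survey item may never feed it. In addition, each survey records every treatment with dates two questions later, and the registry link adds treatment type and dates, including PGA and AS. AS-only men can therefore be set apart with no change to the survey. Section 8 plans no comparison of recurrence between groups, and its binary model (for adverse events) has no AS term.

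Much of this stands, and it rules out several stronger readings that a reader might infer:

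- *That a Yes from an AS man cannot be told from recurrence after prostatectomy.* For AS-only men the grid separates them.
- *That the AS rate would be inflated.* This needs a by-group table the plan does not specify and rates it does not give. At equal rates nothing shows.
- *That records can be reached only through the form sent with the 8-month survey.* The closing text asks men to complete a HIPAA form "if you agree to provide authorization for us to review your medical records regarding your prostate cancer and treatment". It does not say this is the only or first request. Section 7.3 requires signed consent, and that form's content is not in the text available for review.
- *That recurrence must leave the primary list, or that only authorised men should form the denominator.* The first is a preference. The second would create a self-selected sample and discard self-report where it is most needed.

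It might also be said that the item is anchored to initial treatment, and that Q11 glosses that term as surgery, radiation or ablation. But Q11 follows Q8 and is skipped by AS men, while the grid presents AS as a treatment. A man who switched could start the clock at either point.

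The reply does not settle the conflict over source, and it does not date or separate a Yes from a treated man or a switcher.

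**Conclusion.** The point holds as a measurement and specification fault. A primary endpoint has two sources that contradict each other. The only survey items that could supply it cannot separate recurrence from progression in treated men, or in men who moved from AS to treatment before the survey. AS progression could therefore be counted as recurrence after treatment.

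This rests on two conditions: that self-report feeds the endpoint at least in part, and that some men switch after being told of progression or some treated men answer Yes to mean progression. The documents fix neither condition and give no rates, so size and direction cannot be stated. The 2% to 10% range for prostatectomy is an illustration on assumed inputs. The documents do not show a bias against AS or a planned comparison that would be wrong. The fault should be corrected before the endpoint is tabulated.

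**What to change.** 1. **Source.** Reconcile the Protocol Summary and section 6.1. Name the medical record as the source of the endpoint, with self-report as back-up where records are unavailable, and flag each event that rests on self-report.
2. **Survey items.** Split Q8 (8 months) and Q5 (12 months) into two parts: (a) *has a doctor told you that your cancer came back after surgery, radiation, ablation or another active treatment?* and (b) *has a doctor told you that your cancer got worse while you were on active surveillance?* Give each part a does-not-apply box and a month and year. Ask both of all men, so that those who switched from AS are captured and no new skip is needed.
3. **Classification and reporting.** Add to section 8 that events are classified against the treatment dates in Q10 and Q7. Tabulate recurrence in treated men separately from progression on AS, not as one rate across groups.

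The cost is two slightly longer survey items and a few sentences in the Protocol Summary, 6.1 and 8. Recalled months will sometimes be wrong, but the two-part wording still separates the events. If the surveys are already in the field, only steps 1 and 3 apply. Self-reported Yes answers from treated men and switchers should then be reported as unclassified where no record resolves them.

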## 2) Symptom: Swelling

a. In the 7 days after your initial treatment, how **often** did you have **arm or leg swelling**?

Never       Rarely       Occasionally       Frequently       Almost constantly

b. In the 7 days after your initial treatment, what was the **severity** of your **arm or leg swelling** at its **worst**?

None       Mild       Moderate       Severe       Very severe

c. In the 7 days after your initial treatment, how much did **arm or leg swelling interfere** with your usual or daily activities?

Not at all       A little bit       Somewhat       Quite a bit       Very much

## 3) Symptom: General pain

a. In the 7 days after your initial treatment, how **often** did you have **pain**?

Never       Rarely       Occasionally       Frequently       Almost constantly

b. In the 7 days after your initial treatment, what was the **severity** of your **pain** at its **worst**?

None       Mild       Moderate       Severe       Very severe

c. In the 7 days after your initial treatment, how much did **pain interfere** with your usual or daily activities?

Not at all       A little bit       Somewhat       Quite a bit       Very much

## 4) Symptom: Fatigue

a. In the 7 days after your initial treatment, what was the **severity** of your **fatigue, tiredness, or lack of energy** at its **worst**?

None       Mild       Moderate       Severe       Very severe

b. In the 7 days after your initial treatment, how much did **fatigue, tiredness, or lack of energy interfere** with your usual or daily activities?

Not at all       A little bit       Somewhat       Quite a bit       Very much

12. Have you been hospitalized for complications from your prostate cancer treatment or for any other problems after receiving prostate cancer treatment?

Yes:

a. What was the reason for the hospitalization?

---

b. How many days did you spend in the hospital? \_\_\_\_\_

No

13. Did you perform Kegel exercises after your prostate cancer treatment?

Yes--How often do you (did you) do Kegel exercises?

Once a week or less

Twice a week

More often than twice a week

No

I don't know

14. Did your doctor advise you to do Kegel exercises after your prostate cancer treatment?

Yes--What resources were given to you to help you do Kegel exercises? Check all that apply.

Verbal explanation

Handout

Visit with a Nurse Counselor

Referral to Physical Therapy

None

I don't know

Other: \_\_\_\_\_

No

I don't know

15. Did you experience any (other) complication or unexpected outcome within 3 months after your prostate cancer treatment?

Yes: If yes, please describe: \_\_\_\_\_

No

### **Current Health**

16. In general, would you say your health is:

Excellent

Very good

Good

Fair

Poor

Very poor

***For the next set of questions, please think about your experience during the past 4 weeks.***

#### **Urinary Issues**

17. In the past 4 weeks how often did you leak urine (pee)? (Choose one)

More than once a day

About once a day

More than once a week

About once a week

Rarely or never

18. Which of the following best describes your urinary control (ability to hold pee) **during the past 4 weeks?** (Choose one)

- No urinary control whatsoever
- Frequent dribbling
- Occasional dribbling
- Total control

19. How many pads or adult diapers did you usually use per day to control urine (pee) leakage **during the past 4 weeks?** (Choose one)

- None
- 1 pad per day
- 2 pads per day
- 3 or more pads per day

20. How big a problem, if any, was each of the following **during the past 4 weeks?** (Choose one for each item)

	No problem	Very small problem	Small problem	Moderate problem	Big problem
a. Dripping or leaking urine (pee)					
b. Pain or burning on urination (when peeing)					
c. Bleeding with urination (when peeing)					
d. Weak urine stream (pee) or incomplete emptying					
e. Need to urinate (pee) frequently during the day					

21. Overall, how big a problem was your urinary function (ability to pee) for you **during the past 4 weeks?** (Choose one)

- No problem
- Very small problem
- Small problem
- Moderate problem
- Big problem

### Bowel Issues

22. How big a problem, if any, was each of the following **during the past 4 weeks?** (Choose one response on each line)

	No problem	Very small problem	Small problem	Moderate problem	Big problem
a. Urgency to have a bowel movement (poop)					
b. Increased frequency of bowel movements (poop)					
c. Losing control of your stools (poop)					
d. Bloody stools (blood with poop)					
e. Abdominal/pelvic/rectal pain					

23. Overall, how big a problem were your bowel habits (ability to poop) **during the past 4 weeks?** (Choose one)

- No problem
- Very small problem
- Small problem
- Moderate problem
- Big problem

#### **Sexual Issues**

24. Do you currently use any of the following to help with problems with sexual function? (Choose one response on each line)

		Yes	No
a.	Vacuum suction device		
b.	Penile injections (shots)		
c.	Pills, such as Viagra, Cialis, Levitra, Staxyn, Stendra		
d.	Urethral pellets or suppositories (Muse)		
e.	Penile prosthesis (surgical implant)		
f.	Other (please specify): _____		

25. How would you rate each of the following **during the past 4 weeks?**

(Choose one response on each line)

	Very poor to none	Poor	Fair	Good	Very good
a.	Your ability to have an erection (getting hard for sex)?				
b.	Your ability to reach orgasm (climax)?				

26. How would you describe the usual **QUALITY** of your erections (getting hard for sex) **during the past 4 weeks?**  
(Choose one)

- None at all
- Not firm enough for any sexual activity
- Firm enough for masturbation and foreplay only
- Firm enough for intercourse

27. How would you describe the **FREQUENCY** of your erections (getting hard for sex) **during the past 4 weeks?**  
(Choose one)

- I NEVER had an erection when I wanted one
- I had an erection LESS THAN HALF the time I wanted one
- I had an erection ABOUT HALF the time I wanted one
- I had an erection MORE THAN HALF the time I wanted one
- I had an erection WHENEVER I wanted one

28. Overall, how would you rate your ability to function sexually **during the past 4 weeks?** (Choose one)

- Very poor
- Poor
- Fair
- Good
- Very good

29. Overall, how big a problem was your sexual function, or lack of sexual function, for you **during the past 4 weeks?** (Choose one)

- No problem
- Very small problem
- Small problem
- Moderate problem
- Big problem

30. How often have you been able to ejaculate or "cum" when having sexual activity?

- All the time
- Most of the time
- About half the time
- Less than half the time
- None of the time / could not ejaculate

31. How would you rate the strength or force of your ejaculation?

- As strong as it always was
- A little less strong than it used to be
- Somewhat less strong than it used to be
- Much less strong than it used to be
- Very much less strong than it used to be
- Could not ejaculate

32. How would you rate the amount or volume of semen or fluid when you ejaculate?

- As much as it always was
- A little less than it used to be
- Somewhat less than it used to be
- Much less than it used to be
- Very much less than it used to be
- Could not ejaculate

33. If you have had any ejaculation difficulties or have been unable to ejaculate, have you been bothered by this?

- No problem with ejaculation
- Not at all bothered
- A little bothered
- Moderately bothered
- Very bothered
- Extremely bothered

34. How big a problem **during the past 4 weeks** was each of the following for you? (Choose one response on each line)

	No problem	Very small problem	Small problem	Moderate problem	Big problem
a. Feeling depressed					
b. Lack of energy					
c. Change in body weight					

**For the next set of questions, indicate which best describes your health TODAY.**

[figure not shown]
35. Mark an X on the scale to indicate how your health is today.

This scale is numbered from 0 to 100.

100 means the best health you can imagine.

0 means the worst health you can imagine.

The best health  
you can imagine

Please write the number you marked on the scale in the box:

36. Mobility:

- I have no problems walking
- I have slight problems walking
- I have moderate problems walking
- I have severe problems walking
- I am unable to walk

37. Self-care:

- I have no problems washing or dressing myself
- I have slight problems washing or dressing myself
- I have moderate problems washing or dressing myself
- I have severe problems washing or dressing myself
- I am unable to wash or dress myself

38. Usual activities

(e.g. work, study, housework, family or leisure activities):

- I have no problems doing my usual activities
- I have slight problems doing my usual activities
- I have moderate problems doing my usual activities
- I have severe problems doing my usual activities
- I am unable to do my usual activities

39. Pain / Discomfort:

- I have no pain or discomfort
- I have slight pain or discomfort
- I have moderate pain or discomfort
- I have severe pain or discomfort
- I have extreme pain or discomfort

40. Anxiety / Depression

- I am not anxious or depressed
- I am slightly anxious or depressed
- I am moderately anxious or depressed
- I am severely anxious or depressed
- I am extremely anxious or depressed

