## 1. Protocol Summary

Full Title:	Prostate Cancer Comparative Outcomes of New Conceptual Paradigms for Treatment
Short Title:	PC CONCEPT
Principal Investigators:	[name] MPH; [name] MPH
Study Description:	This study will use a population-based cohort design to study men with newly diagnosed low- and intermediate-risk prostate cancer at high-volume centers in Southern California (SCa) and New York State (NYS). Complications of contemporary treatments for prostate cancer and quality of life outcomes, such as general health, urinary, sexual, and bowel function, cancer anxiety, and treatment regret will be compared and tracked over the course of this study.
Sample Size:	N= 3,657
Enrollment:	This study will enroll 2,378 subjects and screen up to 3,657 subjects.
Study Population:	Subjects will have pathologically-confirmed clinically localized prostate adenocarcinoma with National Comprehensive Cancer Network (NCCN) low (T1-T2a, Gleason 6, Grade Group 1, PSA <10 ng/mL) or intermediate risk (T2b-T2c or, Gleason 7, Grade Group 2 or 3 or PSA 10-20 ng/mL) at one of the selected hospitals in SCa and NYS. Subjects must also have a diagnosis date during the 18-month recruitment window.
Enrollment Period:	18 months
Study Design:	Prospective, observational
Description of Sites	Patient enrollment at 15 sites within SCa and NYS, identified through National Cancer Institute-sponsored Surveillance Epidemiology and End Results (SEER)
Study Duration:	01Oct2020 - 30Nov2023
Participant Duration:	12 months
Primary Objectives:	To measure the self-reported, overall and disease specific health related quality of life (HRQOL) prior to treatment, at 8 months, and 12 months following active surveillance (AS), SBRT, IMRT, PGA, and RP.

To define and compare the rate of adverse events following stereotactic body radiation therapy (SBRT), partial gland ablation (PGA), intensity modulated radiation therapy (IMRT) and radical prostatectomy (RP) among men recently diagnosed with low and intermediate risk prostate cancer.

Primary Endpoints:	Change from Baseline in Patient-Reported Quality of Life as Measured on EQ-5D-5L at 8 Months & 12 Months following Treatment
	Change from Baseline in Patient-Reported Urinary, Sexual, and Bowel Function as Measured on EPIC-26 at 8 Months & 12 Months following Treatment

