### **3.2 Patient Questionnaires – Refer to Appendix A.**

#### **A. Administration**

- **Timing and Frequency** – Baseline questionnaires will be sent to eligible participants for study enrollment. Follow-up questionnaires at 8 months and 12 months will be sent to enrolled participants to ascertain treatment choice and obtain patient-reported outcomes following treatment.
- **Survey method**  
Eligible participants will be mailed a survey packet consisting of a paper copy of the survey, an introductory letter and information sheet, and a postage paid return envelope. In the letter the participant will be informed that, if he wishes, he may also complete the survey online and will be given a code and link to the online survey. All materials will be provided in Spanish and English to those participants with Spanish surnames. Interviewers contacting the men are bilingual.

A modified Dillman method will be used to increase response. This includes follow-up with telephone, mail, and offers of completion of the survey online or by telephone.

Specifically, if no response is received after 2 weeks, the study staff will telephone the participant to determine if he has any questions or concerns and to encourage him to complete the survey. At least 5 calls will be made on different days, times of the day (including evenings), and on weekends to reach the person. Additional follow-up efforts will include sending reminder postcards, re-mailing of the survey packet, sending a reminder letter with the link to the online survey, or offering to do the interview over the telephone.

- **Person Identifiers**

Patient identifiers obtained at the time of rapid case ascertainment will be used to link to the completed registry abstract. The registry variables to be linked to the cases will include: patient demographic data (age, date of birth, race, socio-economic status, quintile of census block of residence, marital status, birthplace), tumor data (PSA, stage, histology, grade, clinical and pathologic Gleason score, extension), treatment data (surgical code, radiation (type), dates of treatments, chemotherapy, and hormone therapy, PGA and AS).

B. Study Instruments – Refer to [Appendix A](#).

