**18. Mark an X on the scale to indicate how your health is **today**.**

[figure not shown]
This scale is numbered from 0 to 100.

100 means the best health you can imagine.

0 means the worst health you can imagine.

Please write the number you marked on the scale in the box.

The best health  
you can imagine

The worst health  
you can imagine

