**For the next set of questions, please think about your experience during the past 4 weeks.**

**Urinary Issues**

19. In the past 4 weeks how often did you leak urine (pee)? (Choose one)

- More than once a day
- About once a day
- More than once a week
- About once a week
- Rarely or never

20. Which of the following best describes your urinary control (ability to hold pee) **during the past 4 weeks?** (Choose one)

- No urinary control whatsoever
- Frequent dribbling
- Occasional dribbling
- Total control

21. How many pads or adult diapers did you usually use per day to control urine (pee) leakage **during the past 4 weeks?** (Choose one)

- None
- 1 pad per day
- 2 pads per day
- 3 or more pads per day

22. How big a problem, if any, was each of the following **during the past 4 weeks?** (Choose one for each item)

	No problem	Very small problem	Small problem	Moderate problem	Big problem
a. Dripping or leaking urine (pee)					
b. Pain or burning on urination (when peeing)					
c. Bleeding with urination (when peeing)					
d. Weak urine stream (pee) or incomplete emptying					
e. Need to urinate (pee) frequently during the day					

23. Overall, how big a problem was your urinary function (ability to pee) for you **during the past 4 weeks?** (Choose one)

- No problem
- Very small problem
- Small problem
- Moderate problem
- Big problem

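### The EQ-5D-5L block changes position and internal order between the 8- and 12-month surveys, so change between those waves could mix real change with a layout effect (minor)

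*Combined protocol and SAP*

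**What the plan says.** The Protocol Summary lists among the primary endpoints "Change from Baseline in Patient-Reported Quality of Life as Measured on EQ-5D-5L at 8 Months & 12 Months following Treatment". Section 3.2 A says that "Follow-up questionnaires at 8 months and 12 months will be sent to enrolled participants", so at each wave one questionnaire serves all treatment groups. Section 8 models the patient-reported outcomes by generalised estimating equations with a time-by-treatment interaction and AS as the reference.

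The two follow-up forms in Appendix A place the EQ-5D-5L differently.

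- First Follow Up Survey (8 months): the function items start at "17. In the past 4 weeks how often did you leak urine (pee" and run to Q34. The 0-100 scale follows as "35. Mark an X on the scale to indicate how your health is today", then the five dimensions as Q36-40.
- Second Follow Up Survey (12 months): the five dimensions come straight after the general-health question (Q12), as Q13-17. The scale follows as "18. Mark an X on the scale to indicate how your health is". Only then do the function items start, at "19. In the past 4 weeks how often did you leak urine (pee", running to Q36.

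The plan gives no reason for the change and no way of handling it in the analysis.

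**The concern.** A rating of overall health can depend on what the respondent has just been asked. At 8 months a man rates his health after 18 numbered questions on leakage, bowel habits, erections, ejaculation and mood. At 12 months he rates it before them. The rating scale also moves from first to last within the block.

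Every man gets one layout at 8 months and the other at 12, so no analysis of these data can separate an order effect from real change. If the function items lower the health rating, scores would be held down at 8 months and released at 12, which looks like recovery. Section 8 already expects that shape for urinary function after surgery, so such an artefact would be easy to accept as real.

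An effect that differs by arm is possible. Section 1.2 expects the arms to differ on the very items that precede the EQ-5D-5L at 8 months. Men on surveillance only, or not yet treated, are also told at 8 months to "please skip to Question 16", so they do not see the symptom and complication questions Q11-15.

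**Working it through.** **Layout.** The printed item numbers settle the order, so it is not an effect of reading the PDF.

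| | 8 months | 12 months |
|---|---|---|
| Function and mood items | Q17-34 (18 questions) | Q19-36 (18 questions) |
| EQ-5D-5L dimensions | Q36-40 | Q13-17 |
| 0-100 scale | Q35, first in block | Q18, last in block |
| Block relative to function items | after | before |

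**Where an order effect would go.** Let the switch of layout shift the 8-to-12-month change by c in the AS arm and by c + d in another arm.

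1. Within-arm change: real change + c in AS, real change + c + d in the other arm.
2. Between-arm difference in change (the time-by-treatment term): real difference + d. The common part c goes into the time main effect.
3. Between-arm difference at one wave: c drops out. The contrast is affected only if that wave's own layout acts differently by arm.

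**Size.** The plan has no figure to reproduce: it states no SD, within-person correlation or order effect for the EQ-5D-5L. What follows is an illustration in SD units. The arm sizes, PGA 280 and AS 300, are from Section 8. The assumptions are equal SD at both waves, correlation rho between waves of 0.5 to 0.8, c and d from 0 to 0.20 SD, no true difference, a two-sided 5% test and a normal approximation.

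SE of PGA versus AS at one wave: sqrt(1/280 + 1/300) = 0.083 SD.

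SE of the difference in change: 0.083 x sqrt(2(1 - rho)). This gives 0.083, 0.064 and 0.053 SD at rho 0.5, 0.7 and 0.8.

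False-positive rate = P(|Z + d/SE| > 1.96), with Z standard normal:

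| d (SD) | rho 0.5 | rho 0.7 | rho 0.8 |
|---|---|---|---|
| 0 | 5% | 5% | 5% |
| 0.05 | 9% | 12% | 16% |
| 0.10 | 23% | 34% | 48% |
| 0.20 | 67% | 87% | 97% |

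For within-arm change in PGA, SE = sqrt(2(1 - rho)/280) = 0.060, 0.046 and 0.038 SD. A common effect c of 0.10 SD would then be declared a change in 39%, 58% and 75% of studies.

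With one layout at both waves, the layout-switch terms c and d are zero and the rates return to 5%.

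**The case against.** The case for leaving this alone is strong on several counts. The endpoint is defined as change from baseline at each wave, not as change between waves. The only hypothesis on overall quality of life in Section 1.2 is PGA versus AS at 12 months, and those men complete the same form in the same order. An effect common to all arms cancels from every between-arm contrast and from the interaction. Section 8 names EPIC-26 sexual function, not the EQ-5D-5L, as the main quality-of-life endpoint. All of this stands, and it limits the severity.

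The baseline survey also contains no EQ-5D-5L items, so change from baseline cannot be computed from these instruments whatever the order. That is a separate and larger problem. It does not remove this one: with these forms, 8-to-12-month change is the only within-man EQ-5D-5L change available, and it is the one tied to layout.

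Three stronger readings are tempting and not supported.

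- A reader might infer that the time-by-treatment term is biased. The documents show only that it could be. Neither an order effect nor a difference by arm is demonstrated.
- A reader might attach a number of points on the 0-100 scale to the effect. Nothing in the documents supports one.
- A reader might extend the point to treatment regret. The regret items come after all the function items at both waves. The difference is that six EQ-5D-5L items intervene at 8 months, and nothing in the documents suggests that this matters.

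**Conclusion.** The point holds as a minor weakness in measurement consistency. The EQ-5D-5L block changes both position and internal order between the follow-up surveys, and any order effect is inseparable from wave. Within-arm 8-to-12-month change could therefore mix real change with layout, and the time-by-treatment term could be biased to the extent that the effect differs by arm.

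The size is unknown. The false-positive rates rest wholly on assumed values of c, d and rho, and the assumed range for the effect includes zero. Within-wave between-arm contrasts, including PGA versus AS at 12 months, are made on one common form and are not affected by the change of layout.

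**What to change.** Before the 12-month form is fielded, give the EQ-5D-5L the same position and internal order in both surveys. One way is to move the 12-month block to after Q36 and before the regret items, with the scale first and the dimensions after it, as at 8 months. The block then follows the same run of 18 function and mood questions at both waves.

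Do not align the forms the other way, by moving the 8-month block to directly after the general-health question (Q16). Treated men reach Q16 straight from the symptom and complication questions Q11-15, which men on surveillance only or untreated skip. That would put an arm-dependent context next to the endpoint.

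The cost is reformatting one form across its paper, online and telephone modes and its English and Spanish versions. It adds no questions for patients.

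If 12-month forms are already in use, do not mix layouts within a wave, because that would damage the contrasts now made on a common form. Instead, rest EQ-5D-5L inference on within-wave between-arm contrasts, state the limitation, and do not interpret the 8-to-12-month EQ-5D-5L trajectory or its time-by-treatment term as recovery.
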